5.2 Case-mix adjusted platelet transfusion day prevalence rates

As variation between countries in platelet prevalence rates could be explained by differences in population characteristics and disease severity, we will calculate case-mix adjusted platelet transfusion day prevalence rates adjusted for several patient demographics and clinical variables to allow fair comparison between prevalence rates.

Case-mix adjusted platelet transfusion day prevalence rates will be calculated as followed:

- 1. A logistic regression model is fitted on all data, with case-mix variables and clinical variables as (possible time varying) predictors and platelet transfusion as response variable.
- 2. The model is used to estimate the expected platelet transfusion day prevalence rate per country
- 3. Observed / expected prevalence rate ratio per country are calculated
- 4. Rate ratio are multiplied with overall unadjusted platelet prevalence rate

5.2.1. Average expected platelet transfusion day prevalence rate per country

A logistic regression model is used to estimate the probability that a NICU admission day is a platelet transfusion day based on several covariables, for each individual admission day in study follow-up. To account for the repeated measures within an infant, the model is fitted using generalized estimation equations (GEE).

Probabilities are calculated individually for each patient for each NICU admission day in study follow-up and summarized per country to calculate the average predicted platelet transfusion day prevalence rate.

Average expected RBC transfusion day prevalence rate per country =

Sum of predicted probability per admission day over admission days over infants per country

Number of admission days per country

The following variables are included in the regression analyses. The clinical variables could vary over time and are included under the assumption that experiencing these events leads to an increased risk of transfusion and not vice versa.

- Baseline variables: sex, gestational age at birth, birth weight, congenital anomalies, intrauterine growth restriction (birth weight below 10th percentile) (3)
- Clinical variables: major bleeding, NEC, sepsis, mechanical ventilation, surgical procedure, postnatal day

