5. ANALYSIS OF STUDY OUTCOME MEASURES DESCRIBING PLATELET USE

5.1 Platelet transfusion day prevalence rates

The prevalence rate is the rate of events (new and recurring events) over a specified time period. The platelet transfusion day prevalence rate in a certain time period is defined as the number of platelet transfusion days per 100 NICU admission days in this period. A platelet transfusion day is defined as any day after birth on which the infant received at least one platelet transfusion.

$$\textit{Prevalence rate} = \frac{\textit{Number of RBC transfusions days during study period}}{\textit{Number of admission days in follow up during study period}} \times 100 \ \textit{days}$$

The platelet transfusion day prevalence rate is calculated in each center and pooled per country. We expect a large between country variability, therefore all prevalence rates are pooled using random effects Poisson models described by Stijnen et al. (2010). This model uses the exact within-study likelihood instead of the approximate normal within-study likelihood which is known to perform better with low event rates and small sample sizes. Additionally, this method does not require the use of an continuity correction in case centers have a prevalence rate of 0 platelet transfusion days. (2) Pooling is done using the function "metarate" of the R-package Meta.

Subgroup rates and overall rate will be presented with 95% confidence intervals in a forest plot. Prevalence rates will only presented on country level.

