5.2.2. Observed / expected prevalence rate ratio per country

The prevalence rate ratio per country is defined as the country's observed platelet transfusion day prevalence (as calculated in section 5.1) compared to the country's average expected platelet transfusion day prevalence rate.

Prevalence rate ratio per country =

Observed platelet day prevalence rate per country

Average expected platelet day prevalence rate per country

Observed / expected prevalence rate ratios will be presented in an observed/expected funnel plot.

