5.2.3 Case-mix adjusted prevalence rates

The standardized platelet transfusion day prevalence rates are defined as the prevalence rate ratio for a country multiplied with the overall unadjusted platelet prevalence rate.

 $\label{eq:case-mix} \textit{Case-mix adjusted prevalence rate per country} = \\ \textit{Prevalence rate ratio per country} * \textit{overall unadjusted platelet prevalence rate} \\$

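### The observed rate is per 100 admission days but the expected rate formula is per day, so the observed/expected ratio as written is 100, not 1, when the two agree (minor)

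*SAP*

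**What the plan says.** Section 5.1 sets the scale of the observed rate in words and in its formula. In words the rate is "defined as the number of platelet transfusion days per 100 NICU admission days in this period", and the formula ends in a multiplication by 100 days.

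Section 5.2.1 turns to the expected rate: "A logistic regression model is used to estimate the probability that a NICU admission day is a platelet transfusion day". The country value is then a quotient whose numerator is "Sum of predicted probability per admission day over admission days over infants per country" and whose denominator is "Number of admission days per country". No multiplier is shown, although the result is called a prevalence rate, the term that 5.1 has already defined per 100 days.

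Section 5.2.2 forms the ratio from "the country's observed platelet transfusion day prevalence (as calculated in section 5.1) compared to the country's average expected platelet transfusion day prevalence rate", which ties the numerator to 5.1. Section 5.2.3 defines the adjusted rate as "the prevalence rate ratio for a country multiplied with the overall unadjusted platelet prevalence rate". Nothing in the SAP rescales the expected rate or removes the 100 from the observed rate.

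**The concern.** The two terms of the ratio are written on different scales: the numerator counts days per 100 admission days, and the denominator is a probability per single day. An analyst who codes the formulas as printed gets a ratio that equals 100, not 1, when practice matches case mix.

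Two outputs depend on this ratio: the observed/expected funnel plot in section 5.2.2, and the case-mix adjusted platelet transfusion day rate, which section 2.1 lists as the second main outcome. On the printed formulas, the level of both would be wrong, and adjusted rates could exceed 100 transfusion days per 100 admission days, which is impossible.

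**Working it through.** The SAP gives no numerical value to reproduce, so the check is algebra on its formulas followed by examples. All counts and rates in the examples are assumed.

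**Inputs for a country**
- O = platelet transfusion days and D = admission days (section 5.1).
- P = sum of the model's predicted daily probabilities (section 5.2.1).
- R = overall unadjusted rate, per 100 days by the 5.1 definition (section 5.2.3).

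**Formulas as written**
1. Observed rate (5.1): 100 × O/D.
2. Expected rate (5.2.1): P/D.
3. Ratio (5.2.2): (100 × O/D) / (P/D) = 100 × O/P.
4. Adjusted rate (5.2.3): (100 × O/P) × R.

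**On a common scale**
- Expected rate: 100 × P/D.
- Ratio: (100 × O/D) / (100 × P/D) = O/P.
- Adjusted rate: (O/P) × R.

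The two versions differ by exactly 100, whatever the data.

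**Examples with D = 2000 per country**

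The overall rate is 60/6000 × 100 = 1.0 per 100 days in the first three rows and 300/6000 × 100 = 5.0 in the last three.

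| O | P | Observed per 100 days | Expected as written | Ratio as written | Ratio, common scale | Adjusted as written | Adjusted, common scale |
|---|---|---|---|---|---|---|---|
| 20 | 20 | 1.0 | 0.01 | 100 | 1.0 | 100 | 1.0 |
| 10 | 15 | 0.5 | 0.0075 | 66.7 | 0.667 | 66.7 | 0.667 |
| 30 | 25 | 1.5 | 0.0125 | 120 | 1.2 | 120 | 1.2 |
| 100 | 100 | 5.0 | 0.05 | 100 | 1.0 | 500 | 5.0 |
| 50 | 75 | 2.5 | 0.0375 | 66.7 | 0.667 | 333.3 | 3.33 |
| 150 | 125 | 7.5 | 0.0625 | 120 | 1.2 | 600 | 6.0 |

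The order of countries is the same under both versions, and so are relative differences: 120/66.7 and 1.2/0.667 are both 1.8.

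**A country whose own rate differs from the overall rate**

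Take an observed rate of 4 per 100 days, a mean predicted probability of 0.04 and an overall rate of 2 per 100 days. As written, the ratio is 4/0.04 = 100 and the adjusted rate is 100 × 2 = 200. On a common scale the ratio is 4/4 = 1 and the adjusted rate is 1 × 2 = 2. The inflation is 200/2 = 100 relative to the correct adjusted rate. Relative to the country's own unadjusted rate it is 200/4 = 50.

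**Pooling**

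Section 5.1 pools centre rates within a country with a random-effects Poisson model, so the observed rate need not equal the crude 100 × O/D. This does not affect the point. If the pooled daily rate is r, the ratio is 100 × r / (P/D) as written and r / (P/D) on a common scale.

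**The case against.** The strongest reply is that the 100 is only a unit of expression. Two transfusion days per 100 days and a daily probability of 0.02 are the same quantity, and with units carried through, their ratio is 1. The SAP uses the same term for both quantities, and the steps in section 5.2 describe ordinary observed/expected standardisation, which needs a common scale. The intent is very probably right. That stands, and it makes this a fault of notation, not of method. It does not remove the conflict, because the printed 5.2.1 formula disagrees with the definition that its own name invokes.

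A second reply is that the multiplier may have been lost when the PDF was read. The 5.2.1 formula came through as separate lines without a fraction bar, so a loss cannot be fully excluded. Its numerator and denominator are both present, however, and the surrounding prose speaks only of averaging probabilities. This lowers confidence but does not settle the matter.

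A third reply is that the overall rate in 5.2.3 could be entered as a daily proportion. The adjusted rate would then come out correctly per 100 days. That would depart from the 5.1 definition and leave the ratio and the funnel plot 100 times too large.

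Finally, the slip gives itself away: ratios near 100 and impossible adjusted rates would prompt a check. It resembles the red-cell labels left in the platelet formulas of 5.1 and 5.2.1. This is a fair argument for a low grading.

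**Conclusion.** The point holds as a minor error in a stated formula. Read literally, sections 5.1, 5.2.1 and 5.2.2 give a ratio of 100 × O/P instead of O/P. A country with observed equal to expected then has an adjusted rate of 100 times the overall unadjusted rate instead of that rate itself. The factor is exactly 100 for every country and does not depend on the assumed examples. The finding rests on the 5.2.1 formula being complete as read.

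Three stronger readings are not supported:
- A reader might infer that country comparisons would be biased. They would not be, because a constant factor changes neither ranking nor relative differences.
- A reader might infer that each country's adjusted rate becomes 100 times its own unadjusted rate. Section 5.2.3 multiplies by the overall rate, so this is true only of a country with observed equal to expected whose own rate also equals the overall rate.
- A reader might infer that published adjusted rates will be a hundredfold wrong. The SAP shows only how the formula is written, and an analyst would probably correct it. Section 5.2.2 also prints no numerical reference line for the funnel plot; a reference of 1 is the natural reading, not a stated one.

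**What to change.** In section 5.2.1, write the expected rate as the country's sum of predicted probabilities divided by its admission days, × 100. Alternatively, drop the factor 100 from the observed rate used in section 5.2.2, so that both terms are per day, and keep the overall rate in 5.2.3 per 100 days. In either case, give the unit of each term in 5.2.1 to 5.2.3 and state that a ratio of 1 means observed equals expected, for use as the funnel plot reference.

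The cost is one factor in one formula and a sentence on units. No new data or analysis is needed.

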4.2 Missing data

Missing values were limited in the eCRF since the majority of the collected variables were marked as mandatory to fill in. Therefore, we expect very few missing values in the dataset.

We decided in advance how to handle missing data for the following variables:

Variables	Commentary			
Platelet count prior to transfusion	Only recorded if platelet count was available in the 24 hours before transfusion. If left blank, the value is recorded as 'not available'.			
Platelet count after transfusion	Only recorded if platelet count was available in the 24 hours after transfusion. If left blank, the value is recorded as 'not available'.			
Congenital anomalies	If not recorded, we assume that congenital anomalies were unlikely and the value is recorded as '0'.			
Bleeding disorders	If not recorded, we assume bleeding disorders were not present and the value is recorded as '0'.			
Major bleeding	If not recorded we assume no major bleeding occurred and the value is recorded as '0'.			
NEC	If not recorded, we assume no NEC occurred and the value is recorded as '0'.			
Sepsis	If recorded as unknown, we assume no sepsis occurred and the value is recorded as '0'.			
Mechanical ventilation	If recorded as unknown, we assume no mechanical ventilation occurred and the value is recorded as '0'.			
Surgical procedures	If recorded as unknown, we assume no surgical procedures occurred and the value is recorded as '0'.			

For all other variables, the total number of missing values will be reported, with the number of infants who had one or more missing values for the variable.

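### Bleeding disorders have a missing-data rule but are left out of the case-mix model and the patient characteristics without a reason, so the country O/E ratios may be biased

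*SAP*

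**What the plan says.** Section 4.2 opens its table of rules with "We decided in advance how to handle missing data for the following variables". Nine variables follow. One is bleeding disorders, on a row separate from major bleeding: "If not recorded, we assume bleeding disorders were not present and the value is recorded as '0".

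Section 5.2 gives the aim of the case-mix model: rates are to be "adjusted for several patient demographics and clinical variables to allow fair comparison between prevalence rates". Section 5.2.1 then lists the predictors in two groups:

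- "Baseline variables: sex, gestational age at birth, birth weight, congenital anomalies, intrauterine growth restriction"
- "Clinical variables: major bleeding, NEC, sepsis, mechanical ventilation, surgical procedure, postnatal day"

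Bleeding disorders are in neither group. They are also absent from the event definitions in section 4.3, the patient characteristics in section 4.4 and the outcome analyses in sections 5 and 6. Sections 5.2.2 and 5.2.3 divide each country's observed rate by its expected rate and multiply the ratio by the overall unadjusted rate.

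**The concern.** The case-mix adjusted rate is the second main outcome. It is meant to separate differences in patients from differences in practice. The expected rate reflects only the predictors in the model, so any patient risk they do not capture stays in the O/E ratio and reads as practice in the funnel plot and the adjusted rates.

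A bleeding disorder is a baseline patient feature that could plausibly affect the decision to give platelets, and the study has the data. Because section 4.4 leaves it out as well, a reader of the results could not see whether countries differ on it, and so could not judge whether the omission matters.

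**Working it through.** **1. The variable lists side by side.** The SAP states no figure on this point, so there is nothing to reproduce. The nine rows of the section 4.2 table divide as follows:

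| Section 4.2 row | In 4.4 | In the 5.2.1 model |
|---|---|---|
| Platelet count before and after transfusion (two rows) | no; analysed in 6.3 and 6.4 | no; transfusion-level data |
| Congenital anomalies | yes | yes |
| Major bleeding | yes | yes |
| NEC | yes | yes |
| Sepsis | yes | yes |
| Mechanical ventilation | yes | yes |
| Surgical procedures | yes | yes |
| Bleeding disorders | no | no |

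Bleeding disorders is the only row that no later section uses.

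**2. Size of a possible bias.** All inputs are assumptions; none is in the SAP.

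- p: share of a country's admission days that come from infants with a bleeding disorder
- q: the same share over all countries
- R: ratio of transfusion-day rates, affected to unaffected infants, given the covariates already in the model

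If practice is identical everywhere and the omitted variable is unrelated to the modelled covariates, the O/E ratio that should be 1 becomes

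O/E = (1 + p(R − 1)) / (1 + q(R − 1)).

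| p | q | R = 1 | R = 2 | R = 5 | R = 10 |
|---|---|---|---|---|---|
| 1% | 0.5% | 1.000 | 1.010/1.005 = 1.005 | 1.04/1.02 = 1.020 | 1.09/1.045 = 1.043 |
| 2% | 0.5% | 1.000 | 1.020/1.005 = 1.015 | 1.08/1.02 = 1.059 | 1.18/1.045 = 1.129 |
| 4% | 1% | 1.000 | 1.04/1.01 = 1.030 | 1.16/1.04 = 1.115 | 1.36/1.09 = 1.248 |

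A country with no affected infants moves the other way. At q = 0.5% its ratio is 1/1.02 = 0.980 for R = 5 and 1/1.045 = 0.957 for R = 10. The adjusted rate is O/E times a constant, so it shifts by the same factor.

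**3. Does major bleeding, already in the model, absorb the effect?** This was checked with an exact calculation for two binary predictors. The assumptions were:

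- the country supplies 8% of all admission days
- 2% of its days are from affected infants, against 0.5% elsewhere
- baseline log-odds of a transfusion day −4.2
- odds ratio 5 for a bleeding disorder and 5 for major bleeding
- major bleeding on 30% of affected and 5% of unaffected days

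The ratio is 1.086 without adjustment for major bleeding and 1.073 with it. If the bleeding disorder acts only through major bleeding (its own odds ratio set to 1), the ratio falls from 1.011 to 1.000. Adjustment therefore removes the part of the effect that runs through recorded bleeds and leaves the rest.

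**The case against.** The strongest reply is that nothing here is contradicted. Section 5.2 promises adjustment for several variables, not for all that were collected, and choosing covariates is a matter of judgement. Section 2 says that separate red cell, platelet and plasma papers are planned, and red cell wording survives in the formulas of sections 5.1 and 5.2.1, so the row in section 4.2 may have been carried over from a shared text. That may be so, but it is conjecture. This SAP limits itself to platelets, keeps the row and gives no reason for not using the variable.

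A reader might infer that countries with more affected infants will look like over-users of platelets. The SAP does not support that. It does not define bleeding disorders, gives no frequency or spread between countries, and states no link with platelet use. Sections 6.2 and 6.3 do not name them among the transfusion indications. If the disorders recorded are not treated with platelets, R is near 1 and there is no bias.

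A reader might also infer that rarity is no reason to leave out a single binary term. That is wrong as well. Stability depends on how many affected infants there are with and without transfusion days, not on the total number of admission days, and separation is possible. If the affected infants sit mainly in one country, the coefficient largely reflects that country's own practice. The expected rate is then pulled towards the observed rate, and a real practice difference may be hidden.

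Lastly, one infant with many transfusion days can move a small country's ratio whatever the cause. That is sampling variability, which the funnel plot is there to display, and it is separate from omitted-covariate bias.

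**Conclusion.** The point stands as an unexplained gap in the adjustment, with a possible bias of unknown size. An upward bias in countries with more affected infants needs two conditions: bleeding disorders must raise platelet use given the modelled covariates, and they must be unevenly spread. The SAP shows neither and rules out neither.

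In the illustrations the shift is a few percent or less when a country has twice an overall share of 0.5%. It passes 10% only with a larger concentration and a high rate ratio together, such as 2% against 0.5% with R = 10, or 4% against 1% with R = 5. These figures show what the omission could do; they are not estimates for this study.

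**What to change.** Add bleeding disorders (yes/no) to the baseline variables of the GEE model in section 5.2.1, and add the percentage of affected infants, in total and per country, to section 4.4.

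If there are too few affected infants for a stable coefficient, keep the current model, say that this is the reason, and report the O/E ratios with and without these infants as a sensitivity analysis. The with/without comparison also covers the case where affected infants cluster in one country.

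The cost is one model term and one table row, with no new data. The downside is a possibly unstable coefficient for a rare covariate, which one country's practice may drive if cases cluster there.

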5.2.2. Observed / expected prevalence rate ratio per country

The prevalence rate ratio per country is defined as the country's observed platelet transfusion day prevalence (as calculated in section 5.1) compared to the country's average expected platelet transfusion day prevalence rate.

Prevalence rate ratio per country =

Observed platelet day prevalence rate per country

Average expected platelet day prevalence rate per country

Observed / expected prevalence rate ratios will be presented in an observed/expected funnel plot.

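### The observed/expected ratio in SAP 5.2.2 divides a random-effects pooled rate by a day-weighted expected rate, so the two are not on one scale and O/E can differ from 1 for reasons other than case mix or practice

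*SAP*

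**What the plan says.** The case-mix adjusted rate is the second main outcome (SAP 2.1). It is built in three steps.

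- **Observed rate (5.1).** "The platelet transfusion day prevalence rate is calculated in each center and pooled per country", and "all prevalence rates are pooled using random effects Poisson models". The displayed formula in the same section is a plain ratio of transfusion days to admission days. The reason given for random effects is "We expect a large between country variability".
- **Expected rate (5.2.1).** The numerator is "Sum of predicted probability per admission day over admission days over infants per country" and the divisor is "Number of admission days per country". The probabilities come from a logistic model without a centre or country term, and "the model is fitted using generalized estimation equations (GEE"). The working correlation is not stated.
- **Ratio and adjusted rate (5.2.2 and 5.2.3).** The ratio uses the country's "observed platelet transfusion day prevalence (as calculated in section 5.1"). It is then "multiplied with the overall unadjusted platelet prevalence rate". Section 5.2.3 does not say how that overall rate is obtained. The only overall rate that 5.1 describes is the one in the forest plot.

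**The concern.** Indirect standardisation compares observed and expected events on the same person-time. Its reference value of 1 has meaning only if both are averaged in the same way. Here the numerator gives weight to centres and averages on the log scale, while the denominator gives every admission day equal weight on the natural scale.

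A country's O/E then reflects two things besides its transfusion practice relative to case mix: how its admission days are split between centres, and how far those centres differ. Neither is case mix. Section 5.2 introduces the adjustment so that countries can be compared fairly, and 5.2.2 shows the ratios in a funnel plot, which is read against 1. Both uses are weakened. Two countries with the same number of transfusion days, admission days and expected days could appear at different places in the plot.

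**Working it through.** The SAP states no numerical result for this outcome, so there is no figure to reproduce. It also gives no number of centres, centre sizes, between-centre variance or relation between size and rate. All centre data below are assumptions.

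**1. What each side estimates.** Let the log rate of a centre be normal with mean μ and standard deviation τ.
- Random-effects Poisson pooled rate: exp(μ), the median centre.
- Day-weighted mean rate, if centre size is unrelated to rate: exp(μ + τ²/2).
- Ratio of the first to the second: exp(−τ²/2).

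| τ | 0 | 0.3 | 0.5 | 0.7 | 1.0 |
|---|---|---|---|---|---|
| exp(−τ²/2) | 1.00 | 0.956 | 0.882 | 0.783 | 0.607 |

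If size and rate are related this formula no longer applies, because the crude rate leans towards the large centres and the pooled rate does so much less.

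**2. Example countries.** These are maximum-likelihood random-intercept Poisson fits (4001-point grid, several starting values, τ estimated within each country). Rates are per 100 days. If expected days equal observed days, the last column is the O/E ratio the country would get instead of 1.

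| Transfusion days / admission days by centre | Crude | Pooled | Pooled/crude |
|---|---|---|---|
| 30, 15, 10 / 900 each | 55/2700 = 2.04 | 1.88 | 0.92 |
| 27, 9, 3 / 900 each | 39/2700 = 1.44 | 1.06 | 0.73 |
| 13, 13, 13 / 900 each | 39/2700 = 1.44 | 1.44 | 1.00 |
| 20, 15, 12 / 900 each | 47/2700 = 1.74 | 1.74 | 1.00 |
| 20/2000 and 18/600 | 38/2600 = 1.46 | 1.68 | 1.15 |
| 12/600 (one centre) | 2.00 | 2.00 | 1.00 |

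Rows two and three have the same 39 transfusion days in 2,700 admission days, yet their O/E values would be 0.73 and 1.00. Row five shows the reversal. Its centre rates are 1.00 and 3.00, with geometric mean √(1.00 × 3.00) = 1.73, and the pooled rate lies near that. The crude rate is pulled down by the large low-rate centre.

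**3. Simulation of many countries.** Assumptions: 20 countries with 1 to 6 centres, about 700 days per centre (log-SD 0.5), 2 transfusion days per 100 days, identical case mix, 20 replicates per scenario. With identical case mix, a calibrated model gives every country the same expected rate.

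| τ between/within countries | Size–rate correlation | Country pooled/crude (more than one centre), mean | Share of these with pooled above crude | Overall pooled/crude |
|---|---|---|---|---|
| 0.3/0.3 | 0 | 0.97 | 11% | 0.90 |
| 0.5/0.5 | 0 | 0.925 | 10% | 0.79 |
| 0.7/0.7 | 0 | 0.875 | 9% | 0.62 |
| 0.5/0.5 | +0.6 | 0.88 | 2% | 0.675 |
| 0.5/0.5 | −0.6 | 0.99 | 33% | 0.89 |
| 0.3/0.5 | −0.9 | 1.03 | 52% | 1.01 |

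The third column is the distortion of O/E. The means hide the spread: at 0.5/0.5 with no correlation, the 5th and 95th percentiles of the country ratio are 0.72 and 1.02.

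**4. The multiplier.** If the overall rate in 5.2.3 is the pooled one, the last column is a further factor, the same for every country. Over all countries, the mean ratio of the adjusted rate to its value on one scale is then 0.88, 0.75 and 0.56 in the first three scenarios. With crude rates throughout it is 1.00.

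**The case against.** **A crude reading of the numerator is possible.** The formula displayed in 5.1 is a plain ratio, and in an O/E ratio the observed part usually means counts. An analyst might compute it that way and have no problem. This stands as an ambiguity, but 5.1 says that all prevalence rates are pooled with random effects and 5.2.2 refers back to 5.1. Followed as written, the numerator is the pooled rate.

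**The direction is not fixed.** A reader might infer from exp(−τ²/2) that the adjusted rates are always too low, or that countries with more spread between centres always look more restrictive. The document does not support this. It gives no centre sizes, variances or size–rate relation. The error is upward when larger centres have lower rates, and absent with one centre or homogeneous centres.

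**The multiplier is inferred.** A reader might also take as given that 5.2.3 uses a random-effects rate and so quote a shortfall of about a quarter (0.75 at τ of 0.5/0.5). Section 5.2.3 does not say so. Most of that figure would come from a constant common to all countries (0.79), which changes neither their relative positions nor the O/E funnel plot. The part that affects comparison averages 0.925 in multi-centre countries.

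**The outcome is descriptive.** The SAP states no hypothesis test for it, so no error rate is at stake. That limits the consequence, but comparing countries is the stated purpose of this outcome.

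**Conclusion.** The mismatch between numerator and denominator is real and follows from the SAP's own cross-reference. It is a wrong rule for a main outcome, more than a missing detail. A country with observed days equal to expected days need not get O/E = 1. The departure depends on the number, size and spread of its centres.

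The error is usually downward, but its sign in any one country cannot be known from the SAP. In the assumed examples it runs from 27% too low, in a country with a ninefold spread of centre rates, to 15% too high. A milder threefold spread gives 8% too low. These sizes rest on assumed centre data and on estimating the between-centre variance separately in each country, which the SAP does not specify.

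The undefined multiplier in 5.2.3 is a separate and lesser point: if pooled, it moves the level of all adjusted rates but not the comparison between countries.

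**What to change.** - **5.2.2:** define the observed rate as total platelet transfusion days divided by total admission days in the country, on exactly the admission days that enter the expected rate.
- **5.2.3:** state that the multiplier is the crude overall rate on the same admission days.
- **5.2.1:** specify an independence working correlation for the GEE. With an intercept in the logistic model, the estimating equation then makes the predicted probabilities sum to the observed transfusion days, so overall O/E is 1. Other working correlations do not guarantee this. Robust standard errors still account for repeated days within an infant.
- **5.1:** keep the random-effects rates for the forest plot, with a footnote that they differ from the inputs to O/E and why.

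The cost is a few sentences in the SAP and a simpler calculation. No new data are needed. The unadjusted country rates in the forest plot will not match those behind the O/E ratios, hence the footnote.
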